2 RATIONALE

2.1 Investigational drug: Trametinib (Mekenist®)

Trametinib is a reversible, highly selective allosteric inhibitor of MEK1/MEK2 activation and kinase activity. Trametinib interferes with cellular signal-transduction and inhibits cell proliferation by inducing apoptosis in tumor cell lines in vitro and human tumor xenografts in mice. Trametinib has demonstrated anti-proliferative activity against a broad range of tumor cell lines and xenograft models, and the activity of trametinib was most pronounced in human tumor models harboring BRAF-activating variants. Trametinib inhibits ERK phosphorylation leading to Gap-1 (G1) cell cycle arrest and tumor xenograft growth inhibition in vivo following oral dosing.

Subjects will receive oral trametinib daily in continuous 28-day cycles at 0.025 mg/kg/day with a maximum dose of 2 mg. A single dose reduction will be permitted in individual subjects who experience toxicity while still having evidence of clinical benefit and is assessed per the investigator.

This trial will enroll subjects with symptomatic vascular anomalies with causative variants of the Ras/MAPK pathway and evaluate objective response using individualized subject response criteria. Subjects will also be evaluated for toxicity using CTCAE v5.0. Stopping rules for toxicity and response are included in the statistical section.

Trametinib is a MEK inhibitor with safety data in children and adults with promising pre-clinical and clinical data supporting efficacy in subjects with VA and CLA.^{10-12,14,17,29,34,44,45} In summary, this Phase II, non-randomized, interventional, open-label, sub-protocol of the VATCH trial provides trametinib to subjects with Ras/MAPK pathway driven vascular anomalies. This protocol represents the first collaborative multicenter trial for the targeted treatment of children and young adults with vascular anomalies driven by Ras/MAPK pathway activation.

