4.3.1 Dosing

Eligible subjects will be treated with trametinib administered at 0.025 mg/kg/dose (or 0.0125mg/kg/dose for critically ill subjects, infants < 10kg at enrollment, or based on clinical discretion) daily given orally by tablet or by oral solution via a nasogastric tube (NGT) or gastric tube (GT) at dose level 1 for each disease strata. Dosing will be daily on a continuous 28-day cycle, for up to 24 total cycles. Dosing will be based on weight in kilograms (kg) obtained within 7 days of starting each cycle or pre-determined dosing weight in those subjects whom fluid status fluctuates. The total daily trametinib dose should not exceed the adult dose (2mg) in any subject.

Refer to [Section 10](#) for dose modifications for toxicity.

Trametinib formulations include:

Powder for oral solution: The liquid concentration is 0.05 mg/mL. Doses of trametinib oral solution will be rounded to nearest 0.1mL (0.005 mg) for doses ≤ 0.11 mg (in oral syringes ≤ 3 mL), 0.2 mL (0.01mg) for doses > 0.11 mg (in oral syringes of 5-10 mL volume). Trametinib pediatric oral solution formulation will be administered with a graduated syringe.

Tablet formulation: Doses of tablet formulation should be rounded to the nearest 0.5mg. It is recommended that subjects drink 4 to 6 mL of water/kg body weight following dosing.

A dosing nomogram ([see Appendix II](#)) based on weight and dose level will be used to prescribe trametinib to minimize inter-subject dosing variability. If vomiting occurs after taking the oral solution formulation, the dose should not be repeated, and next dose given at its scheduled time.

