10.2.3 Dose Modifications for Non-Hematologic Toxicity

If a subject experiences a dose-modifying non-hematologic toxicity as defined in [Section 10.2.1](#), the treatment will be held.

If the toxicity does not resolve to meet inclusion/exclusion parameters or baseline within 14 days of drug discontinuation the subject must be removed from protocol therapy unless specifically documented in toxicities of special interest [Section 10.2.6](#).

If the toxicity resolves to meet inclusion/exclusion parameters or baseline within 14 days of drug discontinuation the subject may resume treatment with a reduction to the next lower dose according to [Appendix II](#). See [Appendix II](#) for dosing modification in subjects receiving oral solution or the specified dose reduction in subjects receiving tablets.

- Doses reduced for toxicity will not be re-escalated, even if there is minimal or no toxicity with the reduced dose, unless otherwise specified in the toxicities of special interest [Section 10.2.6](#).
- If the same dose-modifying toxicity recurs in a subject who has resumed treatment, the subject must be removed from protocol therapy.

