10.2.6.1 Treatment Dose Modifications and Guidelines for Rash

Dermatologic complications are the most frequent adverse events in subjects receiving trametinib and so both proactive/prophylactic ([Section 10.1.6.2](#)) and reactive ([Section 10.1.6.3](#)) approaches will be taken. Rashes associated with trametinib have included many different types and can begin as early as cycle 1 or 2. Descriptions include: erythematous rash, maculopapular rash, pruritic rash, acneiform dermatitis, exfoliative rash. Grade 3 rashes are often associated with pruritus and can have scaling. Based on the experience on the current adult Phase I/II study the following recommendations should be followed. For Grade 3 rash trametinib should be held until resolution to Grade 1 or better and then treatment can be resumed at a reduced dose as outlined in the dose reduction table ([Appendix II](#)). For eczematous rashes, moisturizers or low-dose topical corticosteroids may be used if based on the rash appearance they would be considered appropriate treatment. For pustular rash, topical clindamycin gel or lotion may be applied twice daily. For more severe cases, oral tetracyclines may be useful in older children. Ketoconazole shampoo may be used for scalp rash. If oral corticosteroids are required for severe rash, trametinib should be held until improvement to < Grade 1 at a reduced dose as outlined in the dose reduction table ([Appendix II](#)).

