APPENDIX II: DOSING NOMOGRAM

Trametinib dosing will be weight based. The drug is supplied in tablet form or in oral solution form. Dosing nomogram for tablet formulation below. **The maximum dose is 2 mg per day.**

Note: If switching from trametinib solution to trametinib tablets or vice versa in subjects requiring dose reduction, match up the subject's starting dose to ensure the proper dose reduction is being made.

Subject Weight ≥ 35 kg Formulation: Trametinib Tablets 0.5 mg and 2 mg						
Dose Level	Dose Level 1: 0.025 mg/mg/dose once daily Maximum Dose 2 mg Daily			Dose Level -1: 0.020 mg/mg/dose once daily Maximum Dose 1.5 mg Daily		
Weight [#] (kg)	Dose	Number of 0.5 mg Tablets	Number of 2 mg Tablets	Dose	Number of 0.5 mg Tablets	Number of 2 mg Tablets
35 – 50	1 mg	2	0	Oral Solution only 0.75 mg (15 mL)		
50.1 – 70	1.5 mg	3	0	1 mg	2	0
≥ 70.1	2 mg	0	1	1.5 mg	3	0

[#] Weight measured within 7 days of the start of a cycle or pre-determined dosing weight in those subjects whom fluid status fluctuates.

Formulation: Trametinib Oral Solution (0.05 mg/mL)				
Dose Level	Dose Level 1: 0.025 mg/mg/dose once daily Maximum Dose 2 mg Daily		Dose Level -1: 0.020 mg/mg/dose once daily Maximum Dose 1.5 mg Daily	
Weight [#] (kg)	Dose	Volume of Oral Solution	Dose	Volume of Oral Solution
9.0-9.9kg	0.12 (0.0125mg/kg)	2.3mL	0.18mg	3.6mL
10.0-10.9kg	0.2mg	4mL	0.2mg	4mL
11-11.9	0.25mg	5mL	0.22mg	4.4mL
12-13.9	0.3mg	6mL	0.24mg	4.8mL
14-15.9	0.35mg	7mL	0.28mg	5.6mL
16-17.9	0.4mg	8mL	0.32mg	6.4mL
18-19.9	0.45mg	9mL	0.36mg	7.2mL
20-22.9	0.5mg	10mL	0.4mg	8mL
23-24.9	0.6mg	12mL	0.46mg	9.2mL
25-29.9	0.7mg	14mL	0.5mg	10mL
30-34.9	0.8mg	16mL	0.6mg	12mL
35 – 50	1 mg	20 mL	0.75 mg	15 mL
50.1 – 70	1.5 mg	30 mL	1 mg	20 mL
≥ 70.1	2 mg	40 mL	1.5 mg	30 mL

Weight measured within 7 days of the start of a cycle or pre-determined dosing weight in those subjects whom fluid status fluctuates.

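### Two of the 14 oral-solution rows in Appendix II give no usable dose reduction: Level 1 and Level -1 are equal at 10.0-10.9 kg, and at 9.0-9.9 kg the half dose sits in the full-dose column

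*Protocol*

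**What the plan says.** Section 4.3.1 says a nomogram "based on weight and dose level will be used to prescribe trametinib to minimize inter-subject dosing variability", so Appendix II is the operative table. Under section 10.2.3 a subject whose non-hematologic dose-modifying toxicity resolves in time "may resume treatment with a reduction to the next lower dose according to" Appendix II. The hematologic rule (10.2.4) and the rash, retinal-detachment and hypertension rules in 10.2.6 refer to it directly; the CK, pneumonitis and diarrhea rules reach it through 10.2.3.

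The room for reduction is small. Section 2.1 states: "A single dose reduction will be permitted in individual subjects who experience toxicity". Section 10.2.3 adds: "If the same dose-modifying toxicity recurs in a subject who has resumed treatment, the subject must be removed from protocol therapy".

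The oral-solution table has a Level 1 column headed 0.025 and a second column headed "Dose Level -1: 0.020 mg/mg/dose once daily" (the unit is evidently a misprint for mg/kg). In the 9.0-9.9 kg row the Level 1 cell reads "0.12 (0.0125mg/kg") with 2.3 mL, and Level -1 is 0.18 mg with 3.6 mL. In the 10.0-10.9 kg row both columns read 0.2 mg and 4 mL. The tablet table starts at 35 kg, so it offers these children no alternative.

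Sections 2.1.1 and 4.3.1 allow a 0.0125 mg/kg start for critically ill subjects, infants under 10 kg, or by clinical judgement, and mention no approval. Section 10.1.1 names critical illness only, with chair or co-chair approval and a step-up within 3 cycles if tolerated. Appendix IX leaves out clinical judgement. The Abstract leaves dose increases to the treating physician, while 10.1.1 requires approval for 0.032 mg/kg before 6 cycles are complete.

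**The concern.** A dose-reduction table has to give a lower dose in every row. If it does not, the toxicity rules that depend on it cannot work as intended.

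At 10.0-10.9 kg the reduction exists in name only. The child restarts at the dose that caused the toxicity, the single permitted reduction has been used, and recurrence of the same toxicity means removal under 10.2.3. A child could come off a possibly useful drug before any lower dose has been tried.

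At 9.0-9.9 kg the row mixes two starting schemes. An infant started at 0.025 mg/kg has a reduced dose but no printed starting dose. An infant started at 0.0125 mg/kg has a starting dose but no printed lower one, and the neighbouring cell is higher.

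The rows matter because eligibility begins at 2 months and section 4.3.1 expects infants under 10 kg.

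**Working it through.** **Inputs.** Doses and volumes come from the Appendix II oral-solution table. Level rates are 0.025 and 0.020 mg/kg (its headers) and the half dose is 0.0125 mg/kg (4.3.1). The solution is 0.05 mg/mL (4.3.1).

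**Step 1: ratio of Level -1 to Level 1 in every row.**

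| Weight (kg) | Level 1 (mg) | Level -1 (mg) | Ratio |
|---|---|---|---|
| 9.0-9.9 | 0.12 | 0.18 | 1.50 |
| 10.0-10.9 | 0.20 | 0.20 | 1.00 |
| 11-11.9 | 0.25 | 0.22 | 0.88 |
| 12-22.9 (five rows) | 0.30-0.50 | 0.24-0.40 | 0.80 each |
| 23-24.9 | 0.60 | 0.46 | 0.77 |
| 25-29.9 | 0.70 | 0.50 | 0.71 |
| 30-34.9 | 0.80 | 0.60 | 0.75 |
| 35-50 | 1.0 | 0.75 | 0.75 |
| 50.1-70 | 1.5 | 1.0 | 0.67 |
| 70.1 and over | 2.0 | 1.5 | 0.75 |

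Twelve rows reduce the dose by 12% to 33%. The two lightest rows do not reduce it.

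**Step 2: which column is wrong.** From 9.0 to 34.9 kg, every Level -1 cell equals 0.020 mg/kg times the lower end of its band. In particular 0.020 x 9.0 = 0.18 mg and 0.020 x 10.0 = 0.20 mg, so both Level -1 cells are right. The Level 1 cells do not fit their header:

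- 9.0-9.9 kg: 0.025 x 9.0 = 0.225 mg and 0.025 x 9.9 = 0.248 mg, against a printed 0.12 mg. The half dose gives 0.0125 x 9.0 = 0.113 mg to 0.0125 x 9.9 = 0.124 mg, which matches the printed cell and its label.
- 10.0-10.9 kg: 0.025 x 10.0 = 0.250 mg and 0.025 x 10.9 = 0.273 mg, against a printed 0.20 mg. That is 0.2/10.9 = 0.0183 to 0.2/10.0 = 0.0200 mg/kg, which is the Level -1 rate at the bottom of the band.

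**Step 3: is it a reading error from the PDF?** Volumes agree with doses: 3.6 x 0.05 = 0.18 mg and 4 x 0.05 = 0.20 mg. Only 2.3 x 0.05 = 0.115 mg differs slightly from 0.12 mg, which would be 2.4 mL. Scrambled cells would be unlikely to agree this well.

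**Step 4: the 9.0-9.9 kg row for each type of starter.**

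- Started at 0.025 mg/kg (0.225 mg at 9.0 kg): 0.18/0.225 = 0.80, a true 20% cut, but this start is not printed.
- Started at 0.0125 mg/kg (0.12 mg): 0.18/0.12 = 1.50, an increase. No cell in the row is lower.

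More generally, Level -1 at 0.020 mg/kg is 1.6 times the half dose (0.020/0.0125), so the table has no reduced level for a half-dose subject of any weight.

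**Step 5: proposed cells.**

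- 10.0-10.9 kg: 0.25 mg = 5 mL; 0.25/10.9 = 0.0229 to 0.25/10.0 = 0.0250 mg/kg; reduction 0.20/0.25 = 0.80.
- 9.0-9.9 kg: 0.22 mg = 4.4 mL; 0.22/9.9 = 0.0222 to 0.22/9.0 = 0.0244 mg/kg; reduction 0.18/0.22 = 0.82.
- Half dose at 9.0-9.9 kg: 0.12 mg = 2.4 mL, on the step "0.2 mL (0.01mg) for doses > 0.11 mg" in 4.3.1.

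**The case against.** The best defence concerns the 9.0-9.9 kg row. The 0.12 mg cell carries its own 0.0125 mg/kg label, so it can be recognised as the optional low start and not as Level 1, and 0.18 mg is a proper cut from a full start. A reader might infer that the protocol orders a 50% increase after toxicity. The documents do not support that: 10.2.3 speaks of a reduction, and section 10.10 also requires going down a level. The increase happens only if a site reads across the row and ignores both the label and the text. What stands is that the full start is not printed and a half-dose infant has no lower dose.

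A reader might also link rash to removal at 10.0-10.9 kg, since 10.2.6.1 says "Dermatologic complications are the most frequent adverse events in subjects receiving trametinib" and even a persistent Grade 1 rash leads to the table. But 10.2.6.3 has its own stepwise rash rules: Grade 2 rash that recovers returns to the earlier dose, and recurrent intolerable rash leads to another reduction before discontinuation. Mandatory removal is clear for toxicities governed by 10.2.3, not for rash.

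Three further readings go too far. A Level 1 dose below 0.025 mg/kg is not an error in itself, because weight bands cause it elsewhere (0.25/11.9 = 0.0210 to 0.25/11 = 0.0227 mg/kg at 11-11.9 kg; 1/50 = 0.020 mg/kg at 50 kg). The 2.3 mL volume is 4% below 0.12 mg (0.115/0.12 = 0.96), which is rounding. The absence of rows below 9 kg or of a 0.032 mg/kg column is not a mistake either: a starting dose can be calculated, and before the end of cycle 6 the higher dose needs individual approval.

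On the low-start text, a site that always seeks approval satisfies every section, and the Abstract conflicts with 10.1.1 only for 0.032 mg/kg before 6 cycles are complete. That is unclear drafting and a secondary matter.

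**Conclusion.** The point holds for two of 14 oral-solution rows. At 10.0-10.9 kg the printed reduction is 0%, so a child under 10.2.3 can be removed for a recurrent toxicity without a lower dose having been given. At 9.0-9.9 kg the 0.025 mg/kg start is missing, and for a half-dose infant the Level -1 cell is 50% above the starting dose with nothing lower available.

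This assumes that the headers mean mg/kg and that the cells are as printed, which the matching volumes support. The protocol does not give the number of subjects in these weight bands or on the half dose, so the number affected is unknown. The fault concerns dosing and safety and does not enter the sample size or decision rule. It should be corrected because sites act on the table directly.

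**What to change.** 1. At 10.0-10.9 kg, set Level 1 to 0.25 mg (5 mL) and keep Level -1 at 0.2 mg (4 mL). Level 1 then equals that of the 11-11.9 kg row, which is acceptable but should be noted.
2. At 9.0-9.9 kg, print the 0.025 mg/kg start as 0.22 mg (4.4 mL), reducing to 0.18 mg (3.6 mL). Move the 0.0125 mg/kg start to its own labelled entry, 0.12 mg (2.4 mL).
3. For all half-dose subjects, state either a truly lower dose, chosen by the sponsor, or that they stop after a dose-modifying toxicity.
4. As a secondary clean-up, align 2.1.1, 4.3.1, 10.1.1, Appendix IX and the Abstract on who may start at 0.0125 mg/kg, and on the approval needed for that start and for 0.032 mg/kg before the end of cycle 6. Whether infants and subjects started low by clinical judgement must step up within 3 cycles is a clinical decision for the sponsor; the protocol should state it either way.

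The cost is a few corrected cells and some amendment wording, plus one clinical decision on the half-dose reduction. Sample size, endpoint and analysis are unchanged.

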APPENDIX III: MEDICATION DIARY (TABLETS)

Complete each day with the date due, date received, observations, and any comments. Trametinib should be taken by mouth on an empty stomach once a day, at least 1 hour before or 2 hours after a meal. Do not take a missed dose of trametinib within 12 hours of the next scheduled dose. If vomiting occurs within 30 minutes of taking the tablet formulation, the dose of trametinib can be repeated once. Return the diary to your institution at the end of each cycle. Return all unused tablets at the end of each cycle. Store tablets in the refrigerator.

Sites will fill out the cycle, dates and number of prescribed tablets per [Appendix II](#).

Trametinib in the Treatment of _____

Cycle _____	

	

Patient Name		DOB

Drug	Dosage	Route	Day
Trametinib			

Date Due	Date Received	Week	Day	Dose given	Comments
		1	1		
			2		
			3		
			4		
			5		
			6		
			7		
		2	8		
			9		
			10		
			11		
			12		
			13		
			14		
		3	15		
			16		
			17		
			18		
			19		
			20		
			21		
		4	22		
			23		
			24		
			25		
			26		
			27		
			28		
			29/1		

Each Cycle = 28 days

Observations:

APPENDIX IV: MEDICATION DIARY (ORAL SOLUTION)

Complete each day with the date, time and volume in mL of trametinib oral solution taken. Make note of other drugs and supplements taken. Your doctor will tell you what foods you should avoid. Trametinib should be taken by mouth on an empty stomach once a day, at least 1 hour before or 2 hours after a meal. Do not take a missed dose of trametinib within 12 hours of the next scheduled dose. If vomiting occurs after taking oral solution formulation, the dose should NOT be repeated and the next dose should be administered at the regularly scheduled time. Return the completed diary to your institution at the end of each treatment cycle. Please return all unused solution at the end of each cycle. Store the solution at room temperature (25°C or 77°F).

Immediately prior to the removal of dose for administration swirl the bottle of solution gently 2-3 times, if any foam appears allow the bottle to sit for at least 1 minute for the foam to dissipate. Remove the required dose using a suitable graduated syringe:

- a. Ensure that the syringe plunger is fully pushed into the barrel.
- b. Insert the syringe tip into the Adapter, then invert the bottle and dispense at least 5 mL of solution into the syringe and then pump the entire solution back into the bottle to purge the syringe of any air bubbles. Repeat this step until the syringe is free from air bubbles.
- c. Withdraw the required dosing volume. Then re-invert the bottle and remove the syringe from the Adapter and administer the dose to the subject as soon as possible.

Sites will fill out the cycle, dates and the volume of prescribed solution per day per [Appendix II](#).

Trametinib in the Treatment of _____

Cycle _____	

 Patient Name	

 DOB
-------------	--	---

Drug	Dosage	Route	Day
Trametinib			

Date Due	Date Received	Week	Day	Dose given	Comments
		1	1		
			2		
			3		
			4		
			5		
			6		
			7		
		2	8		
			9		
			10		
			11		
			12		
			13		
			14		
		3	15		
			16		
			17		
			18		
			19		
			20		
			21		
		4	22		
			23		
			24		
			25		
			26		
			27		
			28		
			29/1		

Each Cycle = 28 days

Observations:

APPENDIX V: BLOOD PRESSURE

Blood Pressure Levels for Children by Age and Height Percentile

Blood pressure (BP) levels for Boys:

Age (years)	BP Percentile	Systolic Blood Pressure, mm Hg							Diastolic Blood Pressure, mm Hg						
		Percentile of Height							Percentile of Height						
		5th	10th	25th	50th	75th	90th	95th	5th	10th	25th	50th	75th	90th	95th
1	95th	98	99	101	103	104	106	106	54	54	55	56	57	58	58
2	95th	101	102	104	106	108	109	110	59	59	60	61	62	63	63
3	95th	104	105	107	109	110	112	113	63	63	64	65	66	67	67
4	95th	106	107	109	111	112	114	115	66	67	68	69	70	71	71
5	95th	108	109	110	112	114	115	116	69	70	71	72	73	74	74
6	95th	109	110	112	114	115	117	117	72	72	73	74	75	76	76
7	95th	110	111	113	115	117	118	119	74	74	75	76	77	78	78
8	95th	111	112	114	116	118	119	120	75	76	77	78	79	79	80
9	95th	113	114	116	118	119	121	121	76	77	78	79	80	81	81
10	95th	115	116	117	119	121	122	123	77	78	79	80	81	81	82
11	95th	117	118	119	121	123	124	125	78	79	80	81	82	82	83
12	95th	119	120	122	123	125	127	127	78	79	80	81	82	82	83
13	95th	121	122	124	126	128	129	130	79	79	80	81	82	83	83
14	95th	124	125	127	128	130	132	132	80	80	81	82	83	84	84
15	95th	126	127	129	131	133	134	135	81	81	82	83	84	85	85
16	95th	129	130	132	134	135	137	137	82	83	83	84	85	86	87
17	95th	131	132	134	136	138	139	140	84	85	86	87	87	88	89

Blood pressure (BP) levels for Girls:

Age (years)	BP Percentile	Systolic Blood Pressure, mm Hg							Diastolic Blood Pressure, mm Hg						
		Percentile of Height							Percentile of Height						
		5th	10th	25th	50th	75th	90th	95 th	5th	10th	25th	50th	75th	90th	95th
1	95th	100	101	102	104	105	106	107	56	57	57	58	59	59	60
2	95th	102	103	104	105	107	108	109	61	62	62	63	64	65	65
3	95th	104	104	105	107	108	109	110	65	66	66	67	68	68	69
4	95th	105	106	107	108	110	111	112	68	68	69	70	71	71	72
5	95th	107	107	108	110	111	112	113	70	71	71	72	73	73	74
6	95th	108	109	110	111	113	114	115	72	72	73	74	74	75	76
7	95th	110	111	112	113	115	116	116	73	74	74	75	76	76	77
8	95th	112	112	114	115	116	118	118	75	75	75	76	77	78	78
9	95th	114	114	115	117	118	119	120	76	76	76	77	78	79	79
10	95th	116	116	117	119	120	121	122	77	77	77	78	79	80	80
11	95th	118	118	119	121	122	123	124	78	78	78	79	80	81	81
12	95th	119	120	121	123	124	125	126	79	79	79	80	81	82	82
13	95th	121	122	123	124	126	127	128	80	80	80	81	82	83	83
14	95th	123	123	125	126	127	129	129	81	81	81	82	83	84	84
15	95th	124	125	126	127	129	130	131	82	82	82	83	84	85	85
16	95th	125	126	127	128	130	131	132	82	82	83	84	85	85	86
17	95th	125	126	127	129	130	131	132	82	83	83	84	85	85	86

Instructions for using this BP Chart:

1. Measure the subject's blood pressure using an appropriate size cuff.
2. Select appropriate chart for female or male subject.
3. Using the "age" row and "height" column determine if the BP is within the ULN.
4. See [Section 10.1.6.9](#) for definition of dose modifying hypertension. See [Section 10.1.6.11](#) for management and grading of hypertension.

Note: For subjects ≥ 18 yrs, ULN BP is 140/90 mmHg.

This table was taken from "The Fourth Report on the Diagnosis, Evaluation, and Treatment of High Blood Pressure in Children and Adolescents" PEDIATRICS Vol. 114 No. 2 August 2004, pp. 555-576.

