10.2.1.1 Non-Hematological Dose-Modifying Toxicity

- See [Section 10.2.6](#) for management guidelines for toxicities of special interest. Note that dose modification or discontinuation of trametinib for toxicity is considered a dose modifying toxicity.
- Any Grade 4 non-hematological toxicity with specific exclusion of:
 - Grade 4 fever/pyrexia that resolves to Grade < 2 within 72 hours with supportive care (anti-pyretics)
- Dose-modifying hypertension will be considered as the following:
 - Grade 4 hypertension,
 - A blood pressure > 25 mm Hg above the 95th percentile for age, height, and gender, confirmed by repeated measurement

Note: if elevated, take 3 serial blood pressure readings from the same extremity with the patient in the same position, separated by at least 5 minutes. Avoid using the lower extremity if possible. Use the mean average of the 3 measurements.

- Any Grade 3 non-hematological toxicity with the specific exception of:
 - Grade 3 nausea and vomiting of less < 3 days duration

- Grade 3 fever or infection < 7 days duration.
- Grade 3 hypophosphatemia, hypokalemia, hypocalcemia and/or hypomagnesemia responsive to oral supplementation within 7 days
- Grade 2 allergic reactions that necessitate discontinuation of study drug will not be considered a dose-modifying toxicity
- Any Grade 2 non-hematological toxicity that persists for ≥ 7 days and is considered sufficiently medically significant or sufficiently intolerable by patients that it requires treatment interruption
- Grade 2 left ventricular ejection fraction disease
- Grade 2 cardiac valvular toxicity (mitral/aortic/tricuspid)
- Grade 2 pneumonitis
- Treatment interruption longer than 14 days due to delayed recovery from toxicity will be cause for dose modification

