10.2.6.9 Treatment Dose Modifications and Guidelines for Hypertension

Increases in blood pressure (BP) have been observed in subjects receiving trametinib. Should initiation of anti-hypertensive therapy be required, single agent therapy (commonly including the calcium channel blockers amlodipine or nifedipine) should be started and the blood pressure should be monitored at least twice weekly until BP is within the 95th percentile for age, height, and gender ([Appendix V](#)).

If subject is already on an anti-hypertensive medication at study enrollment, then their anti-hypertensive therapy should be adjusted (by either adjusting the dose of their current anti-hypertensive medication or by adding another anti-hypertensive agent) according to the algorithm in [Section 10.1.6.11](#).

[figure not shown]

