10.2.6.11 Management of Hypertension

- The upper limit of normal (ULN) is defined as a BP equal to the 95th percentile for age, height, and gender. ([Appendix V](#))
- The NCI CTCAE v5.0 will be utilized to determine the grade of hypertension for reporting purposes.
- Elevated BP measurements should be repeated on the same day to confirm the elevation. Subjects with an elevated BP should have BP measurements performed at least twice weekly until BP is \leq ULN.
- The algorithm below will be used to manage trametinib related hypertension.

- Hypertension should be managed with appropriate anti-hypertensive agent(s) as clinically indicated. It is strongly recommended that nephrology or cardiology be consulted in the evaluation and management of hypertension.

Elevations in BP are based on systolic or diastolic pressures.

†Elevated blood pressure measurements should be repeated on the same day to confirm the elevation. Subjects with elevated BP at any time should have BP measurements performed at least twice weekly until BP is within the ULN.

§ULN is a BP equal to the 95th percentile for age, height, and gender-appropriate normal values ([Appendix V](#)).

*If BP > 25 mm Hg above ULN for age (verified) or Grade 4 hypertension at any time, hold drug. Study drug should also be held for BP ≥ 25 mm Hg above the ULN for 14 days or ≥ 35 mm Hg above baseline for > 14 days. Antihypertensive agents can be used to control hypertension as clinically indicated after study drug is held.

^ Antihypertensive therapy should be prescribed as clinically indicated, including use of multiple anti-hypertensive agents.

#Screening BP as defined in [Section 10.1.6.10](#)

Arm 1 of algorithm:

- If blood pressure (BP) ≤ 95thile for age, height, and gender: continue trametinib at the same dose.

Arm 2 of algorithm:

- If BP ≤ 10 mm Hg above the ULN: continue trametinib at the same dose and recheck the BP within 72 hours.
 - If the BP is ≤ ULN on recheck, continue trametinib at the same dose.

- If the BP remains above the ULN on recheck, then start/adjust antihypertensive therapy and follow Arm 3 of the algorithm from the point that anti-hypertensive therapy is started/adjusted.

Arm 3 of algorithm:

- If BP is 11 to 25 mm Hg above the ULN on ≥ 2 of 3 measurements or > 35 mmHg above baseline on ≥ 2 of 3 measurements, start/adjust anti- hypertensive therapy and continue trametinib at the same dose. Monitor BP at least twice weekly.

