condition, other concomitant events). Although an adverse drug event may rate only as “possibly related” soon after discovery, it can be flagged as requiring more information and later be upgraded to “probably related” or “definitely related”, as appropriate.

Unlikely: A clinical event, including an abnormal laboratory test result, whose temporal relationship to drug administration makes a causal relationship improbable (e.g., the event did not occur within a reasonable time after administration of the trial medication) and in which other drugs or chemicals or underlying disease provides plausible explanations (e.g., the subject’s clinical condition, other concomitant treatments).

Unrelated: The AE is completely independent of study drug administration, and/or evidence exists that the event is definitely related to another etiology. There must be an alternative, definitive etiology documented by the clinician.

10.10 Treatment Dose Modifications and Guidelines for Adverse Event Reporting specific to study drug

Dose modifying hematological and non-hematological toxicities are defined differently. Dose modification or discontinuation of trametinib for toxicity is considered a dose modifying toxicity. Guidelines for management and dose modifications are also provided for the toxicities of special interest.

Trametinib Dose Modification Schedule for Adverse Events

Grade (CTC-AE)*	Schedule
	Grade (CTC-AE)* Dose Modifications
Grade 1 or Grade 2 (Tolerable)	Continue treatment and monitor as clinically indicated.
Grade 2 (Intolerable) or Grade 3	Interrupt therapy until toxicity is grade 0-1 and reduce by one dose level when resuming therapy.
Grade 4	Discontinue permanently, or interrupt therapy until Grade 0 to 1 and Reduce by one dose level when resuming therapy.

* The intensity of clinical adverse events graded by the Common Terminology Criteria for Adverse Events v4.0 (CTC-AE)

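### Appendix V points to a missing definition of dose-modifying hypertension, and the operative passages give both hold and continue for readings near 25 mm Hg above ULN and leave Grade 3 at or below that line unresolved

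*Protocol*

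**What the plan says.** Appendix V is the chart against which sites compare a blood pressure with the ULN. Its step 4 refers to Section 10.1.6.9 "for definition of dose modifying hypertension", and its note sets the adult limit: "For subjects ≥ 18 yrs, ULN BP is 140/90 mmHg".

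Five other places in the Protocol bear on the decision.

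- **Section 10.2.1.1, hypertension bullet.** It opens "Dose-modifying hypertension will be considered as the following" and lists two conditions: Grade 4, or more than 25 mm Hg above the 95th percentile, confirmed on repeat. Its note asks for three serial readings and says "Use the mean average of the 3 measurements".
- **Section 10.2.1.1, general bullet.** Dose-modifying toxicity also includes "Any Grade 3 non-hematological toxicity with the specific exception of" a short list. Hypertension is not on that list.
- **Section 10.2.3.** Any dose-modifying non-hematologic toxicity leads to a hold.
- **Section 10.2.6.11.** Arm 3 begins "If BP is 11 to 25 mm Hg above the ULN on ≥ 2 of 3 measurements" and continues trametinib at the same dose while antihypertensive therapy is started or adjusted. Arm 4 holds drug above +25 but does not say how several readings are combined. Arm 5 deals with Grade 4.
- **Section 10.10, dose modification schedule.** For intolerable Grade 2 or for Grade 3 it says "Interrupt therapy until toxicity is grade 0-1 and reduce by one dose level when resuming therapy".

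**The concern.** A site that follows the chart is sent to a section number that does not exist. When it finds the passages that do govern, two questions have no single answer: whether Grade 3 hypertension at or below 25 mm Hg over ULN is a hold event, and whether three readings are averaged or counted.

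The answer has consequences for the subject. Under 10.2.3 a held subject who recovers resumes at the next lower dose. That dose is not raised again unless the special-interest section provides for it, and the hypertension text provides nothing of the kind. If the same toxicity recurs after resumption, the subject leaves protocol therapy. With 25 sites (Section 4.7.2), the same readings could therefore lead to an unchanged dose at one site and a lasting reduction at another.

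**Working it through.** The plan states no figure to reproduce. The check traces the cross-reference, then applies each rule to the same readings.

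**1. The pointer.** The contents list and the body number the hypertension section 10.2.6.9. That section opens "Increases in blood pressure (BP) have been observed in subjects receiving trametinib" and goes on to starting or adjusting antihypertensive therapy and monitoring. No definition appears in its text. A figure in that section is not shown, so this rests on the text alone. The definition is in 10.2.1.1, so changing 10.1 to 10.2 in the reference would still not lead the reader to it.

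**2. Combining readings.** Inputs are the adult ULN of 140/90 (Appendix V), the +25 line (10.2.1.1) and the 11 to 25 band (Arm 3).

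- Hold line: 140 + 25 = 165 systolic; 90 + 25 = 115 diastolic.
- Arm 3 band: 151 to 165 systolic; 101 to 115 diastolic.
- Rule A (10.2.1.1): hold if the mean excess over ULN is above 25.
- Rule B (Arm 3): continue if at least two of three excesses lie in 11 to 25.

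| Readings | Excess over ULN | Mean excess | Rule A | Rule B |
|---|---|---|---|---|
| 172, 164, 163 (adult systolic) | +32, +24, +23 | 79/3 = 26.3 | hold | continue |
| any age | +20, +24, +40 | 84/3 = 28.0 | hold | continue |
| any age | +24, +25, +27 | 76/3 = 25.3 | hold | continue |

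The overlap is narrow. If two excesses a and b lie in the band, Rule A is also met only when the third exceeds 75 − (a + b). With +24 and +23 the third must exceed 75 − 47 = 28, and +32 does. With +11 and +11 it would have to exceed 75 − 22 = 53. Ordinary scatter produces the overlap only when the subject is already close to +25.

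**3. Grade 3.** Take a hypertension event graded 3 with a pressure 11 to 25 above ULN.

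- General bullet of 10.2.1.1, then 10.2.3: dose-modifying, hold.
- Section 10.10: interrupt, then reduce.
- Hypertension bullet of 10.2.1.1: not dose-modifying, being neither Grade 4 nor above +25.
- Arm 3 of 10.2.6.11: continue at the same dose.

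The Protocol does not print the Grade 3 limits, so the width of this band rests on an assumption. If adult Grade 3 is assumed to start at 160/100, the part inside Arm 3 is 160 to 165 systolic or 101 to 115 diastolic. If it is assumed to start at 150/95, the whole Arm 3 band is affected (151 to 165 or 101 to 115). If Grade 3 always lay above 165/115, this conflict would vanish.

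**The case against.** The strongest reply is that the specific rule governs the general one. Section 10.2.1.1 begins by referring special-interest toxicities to 10.2.6, and hypertension is one of them. It then gives hypertension its own definition. Section 10.2.6.11 uses the CTCAE hypertension grade for reporting, while its arms act on mm Hg and on Grade 4. CPK follows the same pattern: 10.2.6.4 maintains the dose for asymptomatic Grade 3 elevation, although CPK is not an exception in 10.2.1.1. This reading is plausible and may be what was intended. No sentence states it, however, and the special-interest exceptions in 10.2.3 attach to the 14-day removal and to re-escalation, not to the hold.

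On the readings, the core threshold does agree: 10.2.1.1 and the footnote in 10.2.6.11 both hold above +25 or at Grade 4, and Arm 3 itself turns to a hold if pressure rises past +25 on therapy. One could say the hold prevails. But whether 172, 164 and 163 counts as above +25 depends on how the readings are combined, and asking for verification does not settle that.

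The wrong section number belongs to a wider slip, in which several references still read 10.1.6.x for 10.2.6.x. That explains the number. It does not supply a definition at the renumbered target.

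Several stronger readings are tempting and are not supported.

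- *Appendix V as a third, single-reading hold rule.* Steps 1 to 3 only establish whether a pressure is within ULN.
- *A contradiction for readings such as 166, 166 and 152.* Their mean is 161.3 (+21.3), so 10.2.1.1 does not hold. Only one reading (+12) is in the Arm 3 band, and no passage holds on two of three above +25. This shows a gap in Arm 4, not opposite instructions.
- *A share of trial visits.* Simulating three readings (assumed SD 4 to 8 mm Hg) gives a 3 to 10% overlap of Rules A and B when usual pressure is assumed 22 to 28 above ULN. It gives 0 to 0.4% at +15 and 0.0% at +10. The frequency is produced by the assumed centre, and the Protocol gives no distribution of pressures.

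**Conclusion.** The passages are wrong as written and must be reconciled. The pointer leads nowhere, and no statement of precedence resolves Grade 3 hypertension at or below +25. One set of three readings near +25 can also meet a hold rule and a continue rule at once. That last part follows from the Protocol's own numbers; the Grade 3 part assumes that some Grade 3 readings fall at or below ULN + 25.

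The scope is limited to readings near the cut-off and to that Grade 3 band. It bears on dose holds, reductions and removals. A reader might infer that the severe-toxicity stopping rule is affected. It is not, because Section 9.2 counts only Grade 4 hypertension. Nor do the documents support a claim about the cycle 6 response: an effect through delivered dose is conceivable but cannot be sized from them. Which clinical rule is right is not for this review to say.

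**What to change.** Three wording changes, by amendment:

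1. Point Appendix V step 4 to Section 10.2.1.1, where the definition stands.
2. Have the sponsor's clinicians reconcile the general Grade 3 bullet of 10.2.1.1, the Grade 3 row of 10.10 and Arm 3 of 10.2.6.11, and state in one sentence which prevails for hypertension.
3. Use one rule for the number of readings and how they are combined, worded alike in 10.2.1.1 and in Arms 3 and 4.

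The cost is drafting time and the amendment itself. No extra visits, staff or subjects are needed.
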